3.2.2.6 Colonoscopy findings

Diagnosis or diagnostic findings made at colonoscopy will be reported as such and coded using SOC and PT. The colonoscopy findings, when reported, will then be described for incidence by SOC and PT by treatment group.

3.2.3 Missing data and outliers

3.2.3.1 Missing data

No missing value will be replaced, except for the primary analysis where the missing preparation evaluations (because of colonoscopy not done because of inadequate preparation or preparation-related AEs) will be considered as failures.

In the description of qualitative parameters, subjects with a value counted as "missing" at a visit will be identified as subjects being not assessed.

If a value required a retest, the last reliable non-missing value will be taken into account if measured before the first intake of treatment; and the first non-missing reliable value for postbaseline assessments. An assessment will be considered reliable if it is performed without any technical problem and if the result is within the range of plausible values. Any retest or unscheduled assessments performed will be included in the individual subject data listings.

If there is a significant number of missing values for a subject (or if there is confirmed data appearing spurious), a decision will be made following consultation with the sponsor regarding the handling of these data in summaries, prior to database freeze.

Any repeat or additional assessments performed will be included in the individual subject data listings.

3.2.3.2 *Missing or incomplete dates*

In all listings, missing or incomplete dates should be left as they have been recorded. However, for calculation / sorting / assignation based on dates, the following methods will be used:

- The most conservative approach will be systematically considered (i.e. if the onset date of an AE/concomitant medication is missing / incomplete, it is assumed to have occurred during the study treatment phase (i.e. a TEAE for AEs) except if the partial onset date or other data [stop date, ...] indicates differently).
- A missing/incomplete date of medical history or disease diagnosis will be assumed to have occurred before any study treatment.
- If a partial date and the associated information do not allow to state about the assignation to a group / category, all the possible groups / categories will be considered (e.g. a medication with partial start and stop dates could be considered as prior and concomitant treatment).

Where this is possible, the derivations based on a partial date will be presented as superior inequalities (i.e. for an AE started in FEB2004 after the administration performed on 31JAN2004, the days since last dose will be " ≥ 2 ", similarly the duration of ongoing AEs or medication will be " $\geq xx$ " according to the start and last visit dates).

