**PAGE 33/103** 

Committee will be chaired by the principal investigator. Full details of the operating model for this safety data review will be provided in a charter to be produced.

The study may be terminated by the sponsor at any time.

A subject may discontinue participation in the study at any time for any reason (e.g. lack of efficacy, withdrawal of consent, AE). The investigator and/or sponsor can withdraw a subject from the study at any time for any reason (e.g. protocol violation or deviation as defined in Section 12.1.2, noncompliance with the protocol conditions or AE).

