# 4.3 Subject Withdrawal Criteria and Procedures

In accordance with the Declaration of Helsinki (in accordance with the applicable country's acceptance), each subject is free to withdraw from the study at any time. The investigator also has the right to withdraw a subject from the study in the event of concurrent illness, AEs, pregnancy (see Section 8.1.5), or other reasons concerning the health or wellbeing of the subject, or in the case of lack of cooperation. In addition, a subject may be withdrawn from the study as described in Sections 3.6, 5.2.4.2, 6.2 and 8.1.7.

Should a subject decide to withdraw from the study after administration of IMP, or should the investigator decide to withdraw the subject, all efforts will be made to complete and report the observations up to the time of withdrawal as thoroughly as possible. A complete final evaluation at the time of the subject's withdrawal should be made (see Section 5.2.4.2) and an explanation given of why the subject is withdrawing or being withdrawn from the study.

The reason for and date of withdrawal from the study must be recorded on the eCRF. If a subject withdraws consent, every attempt will be made to determine the reason. If the reason for withdrawal is an AE or a clinically significant laboratory test abnormality, monitoring will continue until the event has resolved or stabilised, until the subject is referred to the care of a local health care professional, or until a determination of a cause unrelated to the IMP or study procedure is made. The specific AE or test result(s) must be recorded on the eCRF. All evaluations should be performed, according to the protocol, on the last day the subject receives IMP, or as soon as possible thereafter. If the final visit is conducted more than 47 days after the

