# IPSEN GROUP F-FR-58800-003 CONFIDENTIAL

# PROTOCOL: FINAL (INCLUDING AMENDMENT #6): 02 MARCH 2020

PAGE 37/103

dose of IMP, all safety evaluations will be performed. It is not planned to collect efficacy data after Visit 2.

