#### 10.4.5 Efficacy Evaluation

As indicated in Section 7.1, the primary efficacy variable is the proportion of subjects with successful overall preparation evaluated with the scale (from 1 to 4) of the Cleansing Score as assessed by the colonoscopist.

A successful preparation will be defined as excellent (4) or good (3) preparation.

A failure preparation will be defined as:

- Fair (2) or poor (1) according to bowel cleansing
- Any subject who did not have a colonoscopy based on the investigator's assessment of the cleansing (insufficient faecal output, unclear faecal discharge, etc.) or due to preparation related AEs.
- Any subject for whom cleaning was not adequate for evaluation.
- Any subject for whom rescue treatment (saline enema) was needed.

The proportion of subjects with successful colon cleansing (graded as excellent or good) will be summarised along with the 95% confidence interval (CI) using the standard Wald asymptotic CI. The primary efficacy endpoint will be analysed using a logistics regression model including country as stratified variable, the interaction between country and treatment will be also investigated. The formal hypothesis test result (p-value) for treatment difference will be presented together with a two-sided 95% CI for the difference in success rates. The non-inferiority will be demonstrated if the lower limit of the 95% CI of that difference is higher than -15%.

If the non-inferiority is demonstrated, the superiority will be analysed based upon treatment difference. If the lower limit of the CI is greater than zero, Eziclen®/Izinova® is proven to be superior to the Klean-Prep®.

Secondary efficacy endpoints are presented in Section 7.2.

Results will be tabulated by treatment group and overall using descriptive summary statistics (mean SD, median, interquartiles and ranges) or frequency count with two-sided 95% CI when appropriate.

Time to clear effluent data will be analysed by using survival methods. The results will be presented both in summary tables (number of events, censors, median and interquartile time to event with 95% CI...) and graphically in Kaplan-Meier plots by treatment group and overall. This will be detailed in the SAP.

Other secondary endpoints will be analysed using Cochran-Mantel-Hænszel (CMH) chi-square for count (percentage) adjusting for country effect and two-way analysis of variance (ANOVA) for continuous parameters including treatment, country and their interaction as covariates.

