2.1.1 Modified Intention-To-Treat population (mITT)

The mITT population is:

All randomised subjects who received even a partial dose of study treatment and produced a primary efficacy assessment.

Subjects will be assessed according to their randomised treatment, regardless of the treatment they receive.

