3.2.1.1 Primary efficacy analyses

The primary endpoint of treatment success will be tested sequentially (hierarchical structure) with the first test being non-inferiority test based upon the treatment difference. A rejection of the null hypothesis will trigger superiority testing.

The two hypothesis tests are hierarchically structured so that the second test (superiority) will only be considered if the first test (non-inferiority) is accepted. The superiority test is powered

to detect an absolute difference of 18 %. There is no alpha adjustment for the second test as a result of the hierarchical testing.

The primary efficacy analysis will be based on the mITT population and repeated on the PP population in order to assess the robustness of the results.

The primary efficacy variable is the proportion of subjects with successful overall preparation evaluated with the scale (from 1 to 4) of the Cleansing Score as assessed by the colonoscopist.

A successful preparation will be defined as excellent (4) or good (3) preparation.

A failure preparation will be defined as:

- Fair (2) or poor (1) according to colon cleansing score,
- Any subject who did not have a colonoscopy based on the investigator's assessment of the cleansing (insufficient faecal output, unclear faecal discharge, etc.) or due to preparation related AEs,
- Any subject for whom cleaning was not adequate for evaluation,
- Any subject for whom rescue treatment (saline enema) was needed.

The proportion of subjects with successful colon cleansing (graded as excellent or good) will be summarised along with the 95 % CI using the standard Wald asymptotic CI using the following SAS code:

```
proc freq data=ADCC(where=(PARAM='Successful overall preparation' and MITTFL='Y'));
```

```
table AVALC / missing binomial(level='Yes' cl=wald);
```

by TRTP;

run;

The primary efficacy endpoint will be analysed using a logistic regression model including treatment and country as covariates as well as the interaction between treatment and country if it is significant (i.e. p < 0.10, as interaction tests have low power) using the following SAS code providing the adjusted proportions with their 95 % CI thank to ilink option, and with the option firth in the model with interaction since there might otherwise be a quasi-complete separation of data points affecting the validity of the model:

proc logistic data=ADCC(where=(PARAM='Successful overall preparation' and MITTFL='Y'));

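### Treated subjects with no colonoscopy because of consent withdrawal, lack of cooperation or noncompliance meet no failure criterion and are left out of every analysis of the primary endpoint

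*SAP*

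**What the plan says.** The primary analysis runs on the mITT, which SAP section 2 defines as "All randomised subjects who received even a partial dose of study treatment and produced a primary efficacy assessment". SAP 3.2.3.1 gives the only missing-data rule for that analysis: "No missing value will be replaced, except for the primary analysis where the missing preparation evaluations" that are missing "because of colonoscopy not done because of inadequate preparation or preparation-related AEs) will be considered as failures". SAP 2.5 and Protocol 10.1.1 say the same.

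The failure definition (Protocol 10.4.5; SAP 3.2.1.1; SAP Appendix 1, item 3) has four items:

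- a fair or poor score;
- "Any subject who did not have a colonoscopy based on the investigator's assessment of the cleansing", or because of a preparation-related AE;
- "Any subject for whom cleaning was not adequate for evaluation";
- need for a rescue enema.

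The protocol foresees other exits after the first intake. Section 3.6 lets a subject stop at any time, with withdrawal of consent as one example, and lets the investigator or sponsor withdraw a subject for "noncompliance with the protocol conditions or AE". Section 4.3 adds withdrawal for concurrent illness, AEs, pregnancy, "or other reasons concerning the health or wellbeing of the subject, or in the case of lack of cooperation". None of the failure items names withdrawal of consent, noncompliance or lack of cooperation.

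**The concern.** A refusal that ends in withdrawal can be an effect of the product. The plan accepts that logic for preparation-related AEs, which it counts as failures when they prevent colonoscopy. It does not carry the logic over to a subject who has had enough of the drink and leaves, so the label the site gives the exit decides whether the subject counts.

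There is reason to ask whether such exits are balanced. Only the investigator and colonoscopist are blinded, and subjects receive a product-specific leaflet (Protocol 14.2.2). The Eziclen/Izinova arm drinks 2250 mL. The Klean-Prep arm drinks 70 mL/kg, which is more than 70 x 40 = 2800 mL at the entry weight and is capped at 4000 mL. Protocol 1.1 describes large-volume PEG as often poorly tolerated.

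At stake is a non-inferiority comparison that may leave out product failures from one arm more than from the other, with no planned analysis that would show the effect.

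**Working it through.** **Tracing one subject.** Take a treated subject who withdraws consent before colonoscopy, with no preparation-related AE and no decision that cleansing was too poor.

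- No cleansing grade exists. Table 4 of the protocol schedules the colonoscopy assessment at Visit 2 only, not in the early-withdrawal column.
- No failure item applies, and SAP 3.2.3.1 replaces nothing else.
- mITT: excluded, because no primary assessment was produced.
- PP (SAP 2.1.2): excluded, because colonoscopy is required.
- Identity-link genmod, bootstrap, by-country and subgroup repeats (SAP 3.2.1.1): all restricted to the mITT.
- The secondary cleansing scores are analysed on the ITT set, which does include the subject, but with nothing imputed the subject contributes no value.

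**The plan's own figure.** Inputs from Protocol 10.2: 85% in both arms, margin 15 points, one-sided alpha 0.025, power 90%, 4% dropout or non-compliance.

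n = (1.960 + 1.2816)^2 x 2 x 0.85 x 0.15 / 0.15^2 = 119.1, so 120 per arm, and 120/0.96 = 125. Both stated figures reproduce. The allowance is 5 subjects per arm, 10 in all.

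**Effect on the confidence limit.** Assumptions: 125 treated per arm; about 85% success among those assessed, rounded to whole subjects; the losses shown are all of the unlisted kind; no country adjustment. The lower limit is pE - pK - 1.96 x sqrt[pE(1-pE)/nE + pK(1-pK)/nK]. Under the current rule the lost subjects leave the denominator. In the alternative they stay in as failures.

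| Losses (Eziclen / Klean-Prep) | Current rule | Lower limit | Counted as failures | Lower limit |
|---|---|---|---|---|
| 5 / 5 | 102/120 v 102/120 | -9.0% | 102/125 v 102/125 | -9.6% |
| 5 / 0 | 102/120 v 106/125 | -8.8% | 102/125 v 106/125 | -12.5% |
| 8 / 2 | 99/117 v 105/123 | -9.8% | 99/125 v 105/125 | -14.4% |
| 10 / 0 | 98/115 v 106/125 | -8.6% | 98/125 v 106/125 | -16.0% |
| 2 / 8 | 105/123 v 99/117 | -8.3% | 105/125 v 99/125 | -4.8% |
| 0 / 10 | 106/125 v 98/115 | -9.5% | 106/125 v 98/125 | -3.2% |

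Worked example, 5 / 0 counted as failures: 0.816 - 0.848 = -0.032; SE = sqrt(0.816 x 0.184/125 + 0.848 x 0.152/125) = 0.0472; -0.032 - 1.96 x 0.0472 = -0.125.

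With no Klean-Prep losses, the conclusion first changes at 8 Eziclen losses: 99/125 v 106/125 gives -15.1%, while 7 losses (100/125 v 106/125) give -14.2%.

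**Effect on type I error.** Suppose that, with these exits counted as failures, the true rates are 85% (Klean-Prep) and 70% (Eziclen), exactly at the margin. Exact binomial enumeration of the unadjusted Wald rule gives 2.6% if every treated subject is counted. Under exclusion the rates among those assessed become 0.70/(1 - rE) and 0.85/(1 - rK), where rE and rK are the proportions lost:

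- 4% / 4% lost (Eziclen / Klean-Prep): 2.0%.
- 4% / 0%: 0.70/0.96 = 72.9% v 85%, an apparent difference of -12.1 points; error 8.4%.
- 8% / 0%: 76.1% v 85%, an apparent difference of -8.9 points; error 23.0%.
- 0% / 4%: 70% v 88.5%, an apparent difference of -18.5 points; error 0.4%.

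**The case against.** The strongest reply is that the group is small and much of it is already caught.

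- A reader might infer that refusing to finish the preparation removes a subject. It does not. Protocol 5.2.2 and 6.1 foresee a nasogastric tube, volume not taken is an endpoint in its own right, and a subject who stops drinking but has the colonoscopy is graded. Only those with no colonoscopy are affected.
- Much intolerance will be recorded as an AE. Protocol 8.6 requires cramping, bloating or nausea rated 2 or more to be reported as one, so a cancellation because of such symptoms can fall under preparation-related AEs. A colonoscopy cancelled for poor output is also a failure. This narrows the group, but whether a given exit is recorded as due to the AE or as withdrawn consent is left to the site.
- Subjects are hospitalised, judged willing at entry, and need the procedure clinically. This argues for low numbers, but the plan still allows 4% for dropout and non-compliance.
- A reader might infer that refusal is shown to depend on the arm, or that the rule favours Eziclen/Izinova. The documents give no rates by arm. The one pointer in Protocol 1.1 is to poor tolerance of large-volume PEG, which suggests Klean-Prep losses, and the current rule is then conservative. Protocol 1.1's remark on poor compliance concerns bowel regimens in general.
- A reader might infer that five losses, all on Eziclen, are enough to reverse the result. That needs observed rates already apart: 98/120 v 106/125 (81.7% v 84.8%) gives -12.5%, and 98/125 v 106/125 gives -16.0%. At the planned 85% it does not happen.
- SAP 3.2.4 and 3.2.5 tabulate population exclusions and reasons for discontinuation by treatment group, so losses will be visible. Visibility is not an analysis of their effect on the test.

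What survives is the narrow gap: no planned analysis of the primary endpoint includes these subjects.

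**Conclusion.** The gap holds in its narrow form. A treated subject with no colonoscopy because of withdrawal of consent, lack of cooperation or noncompliance, with no preparation-related AE and no cancellation for poor cleansing, is neither a success nor a failure and appears in no primary or robustness analysis.

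Its size depends on numbers the documents do not give. Balanced losses within the 4% allowance are negligible. With success near 85% among those assessed, the conclusion changes only if about eight or more are lost on Eziclen/Izinova and none on Klean-Prep, which puts most of the allowance for the whole trial into one arm. The direction of any bias is open. Excess Eziclen losses make the rule anti-conservative; excess Klean-Prep losses make it conservative and cost power. All limits are unadjusted Wald limits and the splits are assumptions. The point should be corrected because the repair is cheap, not because a wrong conclusion is likely.

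**What to change.** In SAP 2.5, 3.2.1.1, 3.2.3.1 and Appendix 1 (3), with matching wording in Protocol 10.1.1 and 10.4.5:

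- Analyse the primary endpoint on all randomised subjects who took any dose (the existing ITT set).
- Count a missing cleansing grade as failure unless a reason unrelated to the preparation, such as equipment or scheduling, is documented before unblinding. A withdrawal of consent without such a documented reason counts as failure, so that no exit fits both rules.

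This also removes the tension between an mITT that requires an assessment and a rule that counts some unassessed subjects as failures in that set.

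At minimum, keep the mITT as primary and pre-specify a sensitivity analysis of the non-inferiority test on all treated randomised subjects with every missing grade counted as failure. In either case, tabulate the reasons for no colonoscopy by arm.

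The cost is wording and one extra run, since the withdrawal reason is already on the eCRF (Protocol 4.3). Observed success rates fall slightly and some unrelated withdrawals may be counted as failures. If the rule becomes primary and 4% are lost in each arm with 85% success in the rest, the success rate is 0.85 x 0.96 = 81.6%, and power falls from 90.4% (120 per arm, excluded) to 86.6% (125 per arm, counted).

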3.2.3.3 Outliers

A search of outliers should be performed before the database lock and actions with the sponsor should be defined.

3.2.4 Subject disposition

A listing of the randomisation numbers will be presented by treatment group and subject.

The number and percentage of subjects screened and included in each population will be presented by treatment group for the screened population and by country and centre. In addition, a flow chart will be provided with the number of subjects in each analysis population as well as colonoscopy performed and completed.

A listing of the inclusion and exclusion criteria will be provided by treatment group and subject, and subject eligibility will also be listed.

The reasons for subject exclusions from each population will also be tabulated by treatment group and overall on the randomised population.

A summary table will present the extent of subject exposure in the study for each treatment group by deriving the study duration defined as the number of days from the date of consent to the last study visit.

Listings of dates of assessments (relative day), of hospitalization entry and discharge and of study duration will be presented by treatment group and subject. The number and percentage of subjects at each planned visit during the study will be presented by treatment group and overall for the Safety population.

3.2.5 Withdrawals

Discontinued subjects will be listed and the numbers of subjects who were randomised, performed colonoscopy, discontinued and completed will be tabulated by treatment group and by country. Primary reasons for discontinuation of study treatment will be tabulated.

Number of subjects by visit will be provided by treatment as well as by country.

3.2.6 Demographic and baseline characteristics

The baseline is the last available assessment before administration of the IMP.

All demographic and baseline characteristics will be listed by treatment group and subject.

Summary statistics (n, mean, SD, median, minimum, maximum) or frequency counts will be provided for demographic and baseline characteristics (sex, country, age, age range ([12-14[/ [14-16[/ [16-18[), height, body weight, weight range (]40-50] /]50-60] / >60 kg) and BMI at baseline) by treatment group and overall for the ITT, mITT and PP populations if they differ by more than 10 %. Demographic and baseline characteristics will also be provided by country, age class weight class and sex on the ITT population.

Pubertal stage, if available, measured using Tanner stage for boys and girls will also be described at baseline using frequency counts by sex and overall, by treatment group and overall for the ITT population and mITT population if they differ by more than 10 %. The Tanner Grading Scale [7 & 8] based on a 5-point scale will be used to assess pubertal stage as follows:

43/62

		Ū.
Grade	Description	
	Prepubertal: testes, scrotum, and penis of about same size and	
Tanner I	proportion as in early childhood.	Typically age ≤ 9 years.
	Enlargement of scrotum and testes. Skin of scrotum reddens	
Tanner II	and changes in texture.	Typically age 9 to 11 years.
	Enlargement of penis, at first mainly in length. Further growth	
Tanner III	of testes and scrotum.	Typically age 11 to 12.5 years.
	Increased size of penis with growth in breadth and	
	development of glans. Testes and scrotum larger, scrotal skin	
Tanner IV	darkened.	Typically age 12.5 to 14 years.
Tanner V	Genitalia adult in size and shape.	Typically age ≥ 14 years.

Table 10 Tanner Grading Scale to assess the genital development in male subjects

Table 11 Tanner Grading Scale to assess the pubic hair development in male subjects

Grade	Description	
	Prepubertal: vellus over pubes is not further developed than	
Tanner I	over abdominal wall.	Typically age ≤ 10 years.
	Sparse growth of long, slightly pigmented, downy hair, straight	
Tanner II	or slightly curled, chiefly at base of penis.	Typically age 10 to 11.5 years.
	Considerably darker, coarser, and more curled hair. Hair	
Tanner III	spreads sparsely over junction of pubes.	Typically age 11.5 to 13 years.
	Hair now adult in type, but area covered is still considerably	
Tanner IV	smaller than in adult. No spread to medial surface of thighs.	Typically age 13 to 15 years.
Tanner V	Spread up linea alba (male-type pattern)	Typically age ≥ 15 years.

Table 12 Tanner Grading Scale to assess the breast development in female subjects

Grade	Description	
	No glandular tissue; areola follows the skin contours of the	Typically age ≤ 10 years.
Tanner I	chest (prepubertal).	
	Breast bud forms, with small area of surrounding glandular	Typically age 10 to 11.5 years.
Tanner II	tissue; areola begins to widen.	
	Breast begins to become more elevated, and extends beyond	Typically age 11.5 to 13 years.
	the borders of the areola, which continues to widen but remains	
Tanner III	in contour with surrounding breast.	
	Increased breast size and elevation; areola and papilla form a	Typically age 13 to 15 years.
	secondary mound projecting from the contour of the	
Tanner IV	surrounding breast.	
	Breast reaches final adult size; areola returns to contour of the	Typically age ≥ 15 years.
Tanner V	surrounding breast, with a projecting central papilla.	

Grade	Description	
	Prepubertal: vellus over pubes is not further developed than	
Tanner I	over abdominal wall.	Typically age ≤ 10 years.
	Sparse growth of long, slightly pigmented, downy hair, straight	
Tanner II	or slightly curled, chiefly along labia.	Typically age 10 to 11.5 years.
	Considerably darker, coarser, and more curled hair. Hair	
Tanner III	spreads sparsely over junction of pubes.	Typically age 11.5 to 13 years.
	Hair now adult in type, but area covered is still considerably	
Tanner IV	smaller than in adult. No spread to medial surface of thighs.	Typically age 13 to 15 years.
	Adult in quantity and type with distribution of horizontal (or	
Tanner V	classically "feminine") pattern.	Typically age ≥ 15 years.

Table 13	Tanner	Grading	Scale t	to assess	the pubic	hair develo	pment in	female	subjects
I HOIC IC	1 4111101	Grading	Senie (the puble	man activit	pmene m	remute	Subjects

Moreover, the indication(s) for colonoscopy will also be described using frequency counts by treatment group and overall for the ITT population and mITT population if they differ by more than 10 %. Indications classified under category "Other" in the eCRF will be described as other and will be listed in a separate listing.

Additionally, haematology measured at baseline (including CBC: red blood cell (RBC) count, haemoglobin, haematocrit, mean corpuscular volume (MCV), mean corpuscular haemoglobin (MCH), mean corpuscular haemoglobin concentration (MCHC), white blood cell (WBC) count with differential (neutrophils, lymphocytes, monocytes, eosinophils, basophils, and others), platelet count and international normalised ratio (INR)) will also be described using summary statistics (n, mean, SD, median, minimum, maximum) after standardisation (see section 3.2.2.2 and reference $\underline{6}$) by treatment group and overall for the ITT population.

Moreover, a frequency table will be presented of the number and percentage of subjects with [low, normal or high values] at baseline.

Furthermore, female subjects of child-bearing potential have to perform a pregnancy test prior to baseline and the corresponding information will be listed when available.

